9.3.3 Subject Satisfaction

Subject Satisfaction will be assessed by the subject using the following subjective 5-grade scale as detailed in Table 5. Subject will be instructed: “Rate your level of satisfaction with the effect of study treatment on inflammatory acne lesions by using the following scale”:

Table 5. Subject Satisfaction Scale

Grade	Description
1	Very satisfied
2	Satisfied
3	Neither satisfied nor dissatisfied
4	Dissatisfied
5	Very dissatisfied

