I have read this protocol in its entirety and I agree to all aspects.

Principal Investigator (*Printed Name*)

Signature

Date

Clinical Trial Protocol ATM-2201	Version 2.0 28-Oct-2022	Confidential Page 4/25
-------------------------------------	----------------------------	---------------------------

SYNOPSIS

Version	Version 2.0 (28-Oct-2022)	Study Device	Intradermal needle adapter
Study Number	ATM-2201		
Phase	Proof of Concept	Control Product	Not Applicable
Indication	Inflammatory Acne Lesions	Study Sites	1 site (US)
Title	Intralesional Injections of Triamcinolone for Acne Vulgaris		
Sponsor	ACOM Labs, Inc.		
Study Duration	14 days per subject	Sample Size	~20 subjects
Study Design	
This is an open-label, prospective, single-arm study. Approximately 20 subjects will be enrolled at 1 study site.
 
All subjects will receive standard-of-care intralesional injection with triamcinolone using an intradermal needle adapter at Visit 1 (Day 1). Subjects will then attend in-clinic visits at Visit 2 (24-hours post-injection), Visit 3 (48-hours post-injection), Visit 4 (72-hours post-injection), Visit 5 (Day 7), and Visit 6 (Day 14).
 
Efficacy assessments (target lesion assessments, photography) and safety assessments will be conducted by the Investigator at each study visit. Subjects will conduct lesion pain assessments at each study visit as well as satisfaction assessments at each post-treatment visit.
		
Study Objectives	The objective of this proof-of-concept study is to investigate the safety of using an intradermal needle adapter for performing intralesional injections.		
Inclusion Criteria	
 Outpatient, male or female of any race, 18 years of age or older. Female subjects of childbearing potential must have a negative UPT at Baseline. Diagnosed with facial acne vulgaris. At least one (1) identifiable inflammatory lesion that, in the opinion of the investigator, is clinically indicated for standard-of-care intralesional injection(s) of triamcinolone and for which the research participant has already agreed to have standard-of-care intralesional injection(s) of triamcinolone. Able to follow study instructions and likely to complete all required visits. In good general health as determined by medical history at the time of screening (Investigator discretion). Sign the IRB-approved ICF (including HIPAA authorization) prior to any study-related procedures being performed. 		

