Exclusion Criteria	
 Female subjects who are pregnant or breast-feeding. Known hypersensitivity or previous allergic reaction to any constituent of triamcinolone injection. Active cutaneous viral infection in any treatment area at Baseline. Have concomitant skin disease or infection (other than acne) or presence of skin comorbidities in the areas of skin where study device will be used. History of poor cooperation or unreliability (Investigator discretion). Planning to move out of the area prior to study completion. Subjects who are investigational site staff members or family members of such employees. Exposure to any other investigational /device within 30 days prior to Visit 1. 		
Study Treatment	
Intradermal Needle Adapter: The intradermal needle adapter is an accessory that slips on the end of a standard 32G 0.5" needle and reduces the effective length of the needle to 1mm. The adapter is made of biocompatible 304 Stainless Steel. It is packaged in single use bags and will
		

Clinical Trial Protocol ATM-2201	Version 2.0 28-Oct-2022	Confidential Page 5/25
-------------------------------------	----------------------------	---------------------------

	
be autoclaved or prepared in the standard manner for typical stainless steel instruments used by the Investigator.
 
Triamcinolone for Injection: A commercial supply of triamcinolone for injection will be used for injection. The site will store triamcinolone as per the conditions described in the package insert. A standard 32G 0.5" needle will be fixed to a 1.0 mL luer syringe and the syringe will be loaded with an appropriate volume and concentration of triamcinolone. A total of 0.05 mL to 0.15 mL of triamcinolone 0.5% to 2.5% will be injected into each target lesion. The choice of volume and concentration will be at the discretion of the Investigator as per his clinical judgement. An intradermal needle adapter will then be installed on the needle.
 
At least one (1), and up to three (3) inflammatory target lesions will be selected for intralesional injections of triamcinolone using the intradermal needle adapter.

Blinding	Not applicable

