1 INTRODUCTION

Intralesional injection of corticosteroids is standard of care therapy for stubborn acne lesions. They are typically dosed with triamcinolone acetonide at concentrations of 0.5 mg/mL to 2.5 mg/mL (i.e., 0.5% to 2.5%) in volumes of 0.05 mL to 0.15 mL.

This proof-of-concept study will investigate the safety of using an intradermal needle adapter for delivery of intralesional triamcinolone injections in patients with acne vulgaris. The intradermal needle adapter is an accessory that slips on the end of a standard 32G 0.5" needle and reduces the effective length of the needle to 1mm. The adapter (currently a prototype) is made of biocompatible 304 Stainless Steel and is being developed to allow patients to safely self-inject triamcinolone, rather than depending on injections performed by a physician.

As intralesional triamcinolone injections are standard-of-care, the purpose of this proof-of-concept study is to test the safety of the intradermal needle adapter, not the safety and efficacy of triamcinolone per-se.

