6 SUBJECT NUMBERING, RANDOMIZATION AND BLINDING

This is an open-label, non-randomized, single-group study. All subjects who are enrolled will receive treatment with the study device. Randomization and blinding are not applicable.

All enrolled subjects will receive a 3-digit subject number, starting at 001. Subject numbers will be assigned in ascending order. The subject number will be used to identify the subject throughout the study. Subjects withdrawn from the study will retain their subject number; new subjects will be allocated a new subject number. Screen Failures will not be entered in the eCRF.

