9 STUDY EVALUATIONS

9.1 Visit Procedures

9.1.1 Visit 1 (Baseline; Day 1)

- Written informed consent (incl. HIPAA and California Bill of Rights)
- Inclusion / exclusion criteria
- UPT (if female subject of childbearing potential)
- Medical history and demographics
- Concomitant medications/treatments
- Investigator Assessments
 - *Global Severity Score (GSS)*
 - *Target Lesion Assessments: lesion erythema, lesion severity*
 - *Target Lesion Photography (pre- and post-injection)*
 - *Target Lesion Injection Videography*
- Subject Assessments
 - *Target lesion pain (pre-injection)*
 - *Intralesional injection pain (post-injection)*
- Intralesional injection(s)
- AE Assessment

Clinical Trial Protocol ATM-2201	Version 2.0 28-Oct-2022	Confidential Page 13/25
-------------------------------------	----------------------------	----------------------------

9.1.2 Visits 2 to 6 (24hr, 48hr, 72hr, 7 days±1 day, 14 days±2 days)

- Investigator Assessments
 - *Target Lesion Assessments: lesion erythema, lesion severity, improvement*
 - *Target Lesion Photography*
- Subject Assessments
 - *Target lesion pain*
 - *Subject Satisfaction*
- Concomitant medications/treatments
- AE Assessment

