9.2 Investigator Assessments

9.2.1 Global Severity Score (GSS)

The Investigator will use the following GSS scale to determine subjects' Baseline acne severity (Table 1).

Table 1: Global Severity Score

Score	Grade	Description
0	Clear	Normal, clear skin with no evidence of acne vulgaris
1	Almost Clear	Rare non-inflammatory lesions present, with rare non-inflamed papules (papules must be resolving and may be hyperpigmented, though not pink-red)
2	Mild	Some non-inflammatory lesions are present, with few inflammatory lesions (papules/pustules only; no nodulocystic lesions)
3	Moderate	Non-inflammatory lesions predominate, with multiple inflammatory lesions evident: several to many comedones and papules/pustules, and there may or may not be one nodulocystic lesion
4	Severe	Inflammatory lesions are more apparent, many comedones and papules/pustules, there may or may not be up to 2 nodulocystic lesions

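### The satisfaction question is not limited to the injected lesions, and its ratings cannot be attributed to the needle adapter alone

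*Combined protocol and SAP*

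**What the plan says.** The introduction (Section 1) gives the study's purpose as "to test the safety of the intradermal needle adapter, not the safety and efficacy of triamcinolone per-se".

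Section 9.3.3 scripts the satisfaction instruction: "Rate your level of satisfaction with the effect of study treatment on inflammatory acne lesions by using the following scale". Answers use the five grades of Table 5. The Synopsis (Study Design) calls for "satisfaction assessments at each post-treatment visit", and the heading of Section 9.1.2 gives the times: "Visits 2 to 6 (24hr, 48hr, 72hr, 7 days±1 day, 14 days±2 days".

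The Study Treatment row of the Synopsis has two entries. The first begins "Intradermal Needle Adapter: The intradermal needle adapter is an accessory that slips on the end of a standard" and the second begins "Triamcinolone for Injection: A commercial supply of triamcinolone for injection will be used for injection". Section 6 also uses the word treatment for the device: "All subjects who are enrolled will receive treatment with the study device".

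Section 8.2 has one to three target lesions injected per subject. Section 10 restricts the analysis to descriptive summaries but promises a 95% confidence interval for every outcome.

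**The concern.** A subject can have inflammatory lesions that were not injected. The instruction does not tell such a subject which lesions to consider. One subject may answer about the injected lesions and another about the whole face, and both answers go into the same table. Uninjected lesions follow their own course over 14 days, under whatever acne medication the subject already uses, so they could move a rating in either direction.

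There is also a question of attribution. The study is about the adapter, but the item asks about the result of treatment, and treatment includes the drug. Satisfaction percentages with confidence intervals in the report of an adapter study could be taken for evidence about the device. The interval would reflect sampling variation only; it would show neither which lesions were rated nor which component produced the result.

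**Working it through.** The plan has no figure to reproduce here, so the check is a comparison of sections.

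**Step 1. Which lesions does each measure refer to?**

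| Measure | Section | Lesions referred to |
|---|---|---|
| Erythema, severity, improvement | 9.2.2 | Each injected lesion, one by one |
| Video and photographs | 9.2.2.4, 9.2.2.5 | Each injected lesion |
| Lesion pain VAS | 9.3.1 | Each lesion chosen for injection |
| Injection pain VAS | 9.3.2 | All injected lesions |
| Satisfaction | 9.3.3 | Inflammatory acne lesions, no restriction |

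Satisfaction is the exception among the lesion measures made after treatment. The Global Severity Score is also not lesion-specific, but it is a baseline description only.

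**Step 2. Can uninjected inflammatory lesions be present?** Yes.
- At most three lesions are injected (Section 8.2).
- Section 5.1 requires at least one suitable lesion and sets no upper limit on severity or lesion count.
- Table 1 in Section 9.2.1 describes moderate acne as "several to many comedones and papules/pustules, and there may or may not be one nodulocystic lesion", and the severe grade goes further.
- Section 7.1 prohibits no medication and asks subjects on acne medication to keep their dosing unchanged.

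They need not be present. A subject with mild acne and one to three inflammatory lesions could have all of them injected, and for that subject the wording makes no difference.

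**Step 3. Could the analysis sort this out afterwards?** No. The schedule of events contains no count of inflammatory lesions. The baseline Global Severity Score would show roughly which subjects had other acne to think about, but not which of them thought about it when answering.

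**Step 4. What can the rating be attributed to?** By the Synopsis, study treatment is adapter plus triamcinolone. Every subject receives both, and no lesion is injected without the adapter for comparison. The rating therefore belongs to the combination. Limiting the wording to injected lesions removes the ambiguity of Step 1 but not this one.

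**Step 5. How many ratings?** About 20 subjects (Section 10.1) × 5 visits (Visits 2 to 6) = 100 at most, taking one rating per subject per visit and no missed visits. All would be collected under the unrestricted wording. The number actually distorted lies somewhere between 0 and 100, and the documents hold nothing that narrows this range.

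**The case against.** The strongest reply is that the item asks about what study treatment did, that only the injected lesions received it, and that a sensible subject will answer about those. The plan nowhere says that satisfaction will be read as acceptability of the device. Adverse events are the only listed safety endpoint, nothing is tested, and no sample size depends on this item.

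Much of this stands. Rating uninjected acne is a reading that the wording leaves open, not one that it states, and the consequence is small. What remains is that the plan ties its other measures to the injected lesions and leaves this one untied, although one phrase would settle it.

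A reader might go further, but the documents do not support these inferences:
- *The item rates the drug and leaves out the adapter.* The Synopsis counts the adapter as part of study treatment, and Section 6 speaks of treatment with the device. The item confounds the two; it does not exclude either.
- *Nothing records the subject's view of the injection.* Section 9.3.2 has subjects score injection pain right after the last injection and again ten minutes later. That covers pain, though not satisfaction.
- *A first rating at 24 hours shows that the drug is being rated.* Timing does not decide what is rated, and the item is repeated to Day 14.

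**Conclusion.** The point holds as a minor defect in wording and reporting. The scripted instruction does not confine the rating to the injected lesions, so satisfaction at Visits 2 to 6 may include untreated acne to an unknown extent. Separately, the single-arm design means that these ratings describe adapter plus triamcinolone and cannot be credited to the adapter.

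Up to about 100 ratings are collected under this wording. The first part matters only if some subjects have uninjected inflammatory lesions and some of those answer about them. Eligibility allows the former and the instruction allows the latter; neither frequency is given. A reader might want to express the problem as the share of a subject's lesions that was treated. The documents give no lesion counts, and that share could be 100% for a subject with few lesions, so no such figure is offered.

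The safety objective, the adverse event analysis and the sample size are unaffected. The reason to act before data are collected is that an ambiguous question cannot be repaired in the analysis.

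**What to change.** 1. In the Section 9.3.3 instruction, replace the general reference to inflammatory acne lesions with *the lesion(s) that were injected*, and leave the rest of the sentence and the scale as they are.
2. Add one sentence to Section 10 saying that satisfaction at Visits 2 to 6 is reported as an outcome of the combined treatment, adapter plus triamcinolone, and not as a device result.

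The cost is a protocol amendment agreed by the sponsor and the investigator and approved by the IRB, as Section 3.2 requires for a change to study procedures. No visit or assessment is added. If ratings have already been collected under the present wording, the second change can still be made, and the report should say that the lesions being rated were not specified.

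A separate satisfaction question about the injection at Visit 1 might seem the natural next step. It would be an optional extra and is not needed to settle this point. With no comparison injection, it too would mix adapter, drug, needle and technique, so it should not be presented as the device result.

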9.4 Safety

9.4.1 Adverse Events

All observed or volunteered AEs regardless of suspected causal relationship to the study device will be recorded in the CRF. Subjects will be questioned for the occurrence of any new or worsening signs or symptoms at each visit.

9.4.1.1 Definition of Adverse Event

An AE is any untoward medical occurrence in a patient or clinical investigation subject administered a study device and which does not necessarily have a causal relationship with the study device. AEs include any unfavorable and unintended illness, sign, symptom, clinically significant laboratory test abnormality, or disease temporally associated with the use of a study device that has appeared or worsened during the course of the clinical trial, regardless of causal relationship to the study device under study.

The collection of non-serious AEs and serious adverse events (SAEs) will begin following the subject's signature of the informed consent form.

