2 STUDY OBJECTIVE

The objective of this proof-of-concept study is to investigate the safety of using an intradermal needle adapter for performing intralesional injections.

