8.2 Triamcinolone for Injection

A commercial supply of triamcinolone 10% for injection will be provided to the site and diluted with Saline to the appropriate concentration. The site will store triamcinolone as per the conditions described in the package insert.

A standard 32G 0.5" needle will be fixed to a 1.0 mL luer syringe and the syringe will be loaded with an appropriate volume and concentration of triamcinolone. A total of 0.05 mL to 0.15 mL of triamcinolone 0.5% to 2.5% will be injected into each target lesion. The choice of volume and concentration for each individual lesion will be at the discretion of the Investigator as per his clinical judgement. The intradermal needle adapter will then be installed on the needle.

At least one (1), and up to three (3) inflammatory target lesions will be selected for intralesional injections of triamcinolone using the intradermal needle adapter.

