10.2 Assessment of Safety

10.2.1 Adverse Events

All AEs occurring during the study will be recorded and classified on the basis of MedDRA terminology. Descriptions of AEs will include the date of onset, the date the AE ended, the severity of the AE, the relationship to study medication, the action taken regarding study medication usage, the action taken to treat the AE, and the outcome. All reported treatment-emergent AEs (TEAEs) and treatment-related events (TRAEs) will be summarized by the number of Subjects reporting AEs, system organ class, severity, seriousness, and relationship to study medication.

AEs will be summarized by treatment group and severity, and by treatment group and relationship to study device. Each subject will be counted only once within a system organ class or a preferred term by using the AEs with the greatest relationship within each category.

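### An injury to the person handling the adapter would enter no safety table, although the study's only objective is the safety of using the adapter

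*Combined protocol and SAP*

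**What the plan says.** Section 2 gives one objective: to "investigate the safety of using an intradermal needle adapter for performing intralesional injections". Section 1 calls the adapter a prototype and says that it "is being developed to allow patients to safely self-inject triamcinolone, rather than depending on injections performed by a physician". The synopsis lists adverse events as the only safety endpoint.

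Section 8.2 sets the order of preparation. The needle is attached to the syringe, the syringe is loaded, and only after that: "The intradermal needle adapter will then be installed on the needle". Section 8.1 explains that the adapter slips over the end of the needle. Neither section says who fits it.

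The safety rules refer to subjects throughout:

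- Definition (9.4.1.1): "An AE is any untoward medical occurrence in a patient or clinical investigation subject administered a study device".
- Start of collection (9.4.1.1): it "will begin following the subject's signature of the informed consent form".
- Elicitation (9.4.1): "Subjects will be questioned for the occurrence of any new or worsening signs or symptoms at each visit".
- Tables (10.2.1): treatment-emergent and treatment-related events "will be summarized by the number of Subjects reporting AEs, system organ class, severity, seriousness, and relationship to study medication".
- Population (10.3.1): safety is analysed in the mITT set, that is, enrolled subjects treated at least once with the device.
- Eligibility (5.2, exclusion 7): site staff and their families cannot be subjects.

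**The concern.** Fitting the adapter onto a needle already attached to a loaded syringe is a handling step that an injection without the adapter does not have. An injury at that step is among the harms most clearly due to the adapter, as opposed to the triamcinolone or the intended skin puncture. If it happens to a member of site staff, the plan's own AE rule leaves it out of the only safety endpoint.

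Two things are at stake. First, the study could truthfully state, under its own definitions, that there were no device-related events although the device had hurt the person using it. Second, the intended later use is self-injection, where the person handling the adapter is the patient, so whether it can be handled without injury bears directly on the reason for developing it.

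**Working it through.** The plan states no figure on this point, so there is nothing to reproduce. The check is a trace through the text, followed by arithmetic that shows the scale.

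**Step 1: follow an operator needle-stick through the plan.** Suppose that a staff member is pricked while fitting the adapter correctly.

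- It is not an AE under 9.4.1.1, because it did not occur in a subject. The second sentence of that definition does not repeat the word subject, but it elaborates the first and does not widen the population or the counts.
- It would not be elicited under 9.4.1, which describes questioning subjects. Section 9.4.1.2 also accepts AEs that site personnel observe, but that concerns who notices an event, not who suffers it.
- The operator is not in the mITT population (10.3.1) and cannot be, given exclusion 7. The event therefore has no place in the numerator or denominator of the 10.2.1 tables.

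**Step 2: look for another route to a safety result.**

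- Protocol deviations (10.3.4, 11.3) are departures from procedure. A needle-stick during correct fitting is not one, and one that did involve a departure would be tabulated as a deviation, not as a safety event.
- Videography (9.2.2.4) starts just before the needle enters the lesion, after fitting.
- The Unanticipated Problems form is mentioned only for pregnancy (9.4.1.7).
- Section 3 commits the study to ISO 14155 and to device regulations in general, but the protocol carries no user-injury definition, data item or table into its own text.

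No route puts the event into a safety table.

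**Step 3: number of adapter uses.** Inputs: about 20 subjects (10.1) and 1 to 3 target lesions each (8.2). The plan does not say whether the adapter is fitted once per subject or once per lesion.

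- Fewest: 20 × 1 = 20. This is possible even with three lesions, since 3 × 0.15 mL = 0.45 mL fits one 1.0 mL syringe, unless the concentration differs between lesions.
- Most: 20 × 3 = 60, with three lesions in every subject and one fitting per lesion.

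**Step 4: chance of at least one operator injury.** The formula is 1 − (1 − p)^n, with uses taken as independent. The risk p per use is an assumption; the documents give none.

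| Assumed p | n = 20 | n = 40 | n = 60 |
|---|---|---|---|
| 0.1% | 2.0% | 3.9% | 5.8% |
| 1% | 18.2% | 33.1% | 45.3% |
| 2% | 33.2% | 55.4% | 70.2% |
| 5% | 64.2% | 87.1% | 95.4% |

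For example, with p = 2% and n = 20: 1 − 0.98^20 = 33.2%.

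**Step 5: what a recorded zero would show.** The exact two-sided 95% upper limit for 0 events in n uses is 1 − 0.025^(1/n). This gives 16.8% for n = 20, 8.8% for n = 40 and 6.0% for n = 60. The limits treat uses as independent. At one site, with probably one operator, they are not, so 6.0% is a best case.

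**The case against.** The strongest reply is about scope. Section 1 speaks of using the adapter to deliver injections in patients with acne, which can be read as safety in the treated patient, and a subject-based AE definition fits that reading. For a proof of concept in about 20 subjects, adding operator safety might then be called an extension. Part of this stands: the plan does not contradict itself. But the objective in Section 2 is worded around use of the adapter, and Section 1 gives self-injection as the aim, so harm to the user is hard to treat as outside the question.

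A second reply is that ISO 14155, named in Section 3, may already require user injuries to be recorded. The documents do not show whether it does. What they do show is that the protocol gives such an event no field and no table.

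A third reply is that a few fittings by site staff say little about lay patients. That is fair, and it limits what a zero count could be taken to mean.

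A reader might also infer more than the text supports:

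- *That operator injuries are expressly barred or could appear in no output at all.* No sentence excludes them. The gap follows from the definition, population and counts together, and a needle-stick involving a departure from procedure could appear among the deviations.
- *That fitting injury is the only harm attributable to the adapter.* The adapter sets the effective needle length, so harm to a subject from depth or from contact with the skin could be attributed to it too.
- *That the case report form questions only subjects, that the needle is uncovered at fitting, or that the adapter has to be removed.* The form is not in the documents, a cover is neither mentioned nor ruled out, and no removal step is described.
- *That an injury is likely.* At an assumed 0.1% per use, the chance of seeing one is only 2% to 6%.

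**Conclusion.** The concern holds in this form: under the plan's stated AE rules, an injury to a member of site staff handling the adapter would enter no safety table, in a study whose only objective is the safety of using that adapter. This is more than a missing detail, because following the rules as written produces the omission. It should be corrected, preferably before enrolment, since such an event is best captured on the day.

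The conclusion about the text rests on one assumption: that site staff fit the adapter. The plan assigns the step to nobody, but it describes preparation for injections given at the investigator's discretion and gives subjects no part in it. A subject who fitted the adapter and was injured would be covered by the AE definition.

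The size is uncertain. The per-use risks are assumptions, the number of uses could be anywhere from about 20 to 60, and uses by one operator are not independent. The figures show that an injury could plausibly occur and go unreported in the safety results; they do not show that one is to be expected.

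**What to change.** - **9.4.1.1:** state that any injury or needle-stick to a person handling the adapter is recorded as a device event, separately from subject AEs.
- **Day 1 form:** add one item per adapter use, asking whether the operator was injured (yes or no) and, if so, at what stage. This also records the number of adapter uses, which the plan does not fix.
- **10.2.1:** report the number of uses with an operator injury over the total number of adapter uses, with a short narrative for any event. If an exact 95% CI is given, label it descriptive and note that uses by the same operator are not independent.

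The cost is one sentence, one form item and one table line, with no extra visit or study procedure. There are two downsides. The device-safety report may look slightly less favourable. And with one site and probably one operator, that person may be identifiable, and site staff are not consented subjects. The form should therefore hold no staff identifiers, and the report should give only the aggregate count and a non-identifying narrative.
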